### 11.0 Data Management

- The study will be a double-blinded randomized controlled trial of participants undergoing ACL reconstruction at one academic medical center. Although the anesthesiologist administering the block will not be blinded, the surgeons, participants, and study statistician will be blinded to treatment assignment. Participants will be randomized to receive either ACB or ACB + iPACK block. We will use stratified randomization, stratifying on biologic sex, to ensure similar distributions of male/female participants in each treatment arm the same.
- The primary outcomes of interest are participant reported postoperative pain over time and quadricep strength based on the leg raise and knee extension test. Postoperative VAS pain score reported as average, worst, and least pain will be collected on post-op day 0 (after 12pm), 1 (prior to 12 pm and after 12 pm), and 2 (before 12 pm). The association between postoperative pain with block type will be evaluated using a series of linear mixed models evaluating average pain, worst pain, and least pain as dependent variables. Models will include fixed effects for preoperative pain score, block type, postoperative time, and the interaction between block type and post-operative time and a random subject effect to account for correlation between pain scores collected on the same subject over time. Model assumptions will be checked graphically, and transformations will be considered as needed. The difference in patient reported pain between block type by post-operative time and pain score type will be evaluated using a series of linear contrasts. A similar study

by Amer  $(2018)^1$  comparing combined Adductor Canal and iPACK Blocks versus combined Adductor Canal and Periarticular Injection blocks for pain management in ACL Reconstruction Surgery found a difference in VAS pain scores of 1.5 between 0 to 8 hours post-op and standard deviation in VAS pain of 2.5 units. A sample size of n=35 participants per treatment arm (70 total) with at least 3 measures of pain provides 80% power to detect a difference in pain score of 2 units at significance level  $\alpha=0.004$  (Bonferroni corrected for 4 comparisons) and assuming a compound symmetric covariance structure with a conservative standard deviation = 3.0 and correlation within subject is  $\rho=0.33$ . We will enroll 41 participants (82 total) in each arm to allow for up to 20% attrition.

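### The 0.004 significance level does not follow from the 4 comparisons it is attributed to, and the stated 80% power belongs to a time-averaged difference that is not among the contrasts the plan describes

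*Combined protocol and SAP*

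**What the plan says.** All of this stands in section 11.0 Data Management. Pain is to be analysed with "a series of linear mixed models evaluating average pain, worst pain, and least pain as dependent variables". On content, "Models will include fixed effects for preoperative pain score, block type, postoperative time, and the interaction between block type and post-operative time", plus a random subject effect. The tests are described in one sentence: "The difference in patient reported pain between block type by post-operative time and pain score type will be evaluated using a series of linear contrasts". Four collection times are listed: the afternoon of day 0, the morning and afternoon of day 1, and the morning of day 2.

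The sample size sentence says that 35 participants per arm "with at least 3 measures of pain provides 80% power to detect a difference in pain score of 2 units at significance level" 0.004, which it explains as "Bonferroni corrected for 4 comparisons". It assumes compound symmetry, SD 3.0 and within-subject correlation 0.33. Enrolment is 41 per arm to allow for attrition.

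**The concern.** Two things do not fit together.

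First, the threshold and its explanation disagree. A Bonferroni correction of 0.05 for 4 tests is not 0.004. Someone applying the plan could use either 0.004 or 0.0125, and a p-value between them could be called either way.

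Second, the power statement does not say which contrast it refers to. It relies on at least 3 measures and a within-subject correlation, which points to a difference averaged over time. The contrasts in the analysis text are block differences at each time for each score. The plan does not say whether an averaged difference, any one window or a particular window settles the pain question. A reader may therefore attach the 80% to contrasts that do not have it.

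**Working it through.** **Inputs from section 11.0:** 35 per arm (41 enrolled), difference d = 2, SD 3.0, correlation 0.33, 3 measures, alpha 0.004, 4 times, 3 scores. **Assumed:** family level 0.05; two-sided tests; normal approximation; where stated, a correlation r between preoperative pain and each window, which the plan does not give.

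**1. Threshold.** 0.05/4 = 0.0125. 4 × 3 = 12 and 0.05/12 = 0.0042. Conversely, 12 × 0.004 = 0.048, whereas 4 × 0.004 = 0.016.

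**2. The plan's own 80%.** The variance of a subject's mean over 3 compound-symmetric measures is 9 × (1 + 2 × 0.33)/3 = 4.98.
- SE of the block difference = √(2 × 4.98/35) = 0.5335, and 2/0.5335 = 3.749.
- The critical value at two-sided 0.004 is 2.878. Power = Φ(3.749 − 2.878) = 80.8%.
- n per arm for 80% = 2 × 4.98 × (2.878 + 0.842)²/2² = 34.5, which rounds up to the printed 35.
- At 0.0125 (critical value 2.498) the same formula gives 27.8, that is, 28 per arm.

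So the calculation used 0.004 and a difference averaged over 3 measures. With a t reference on 68 df the power is 77.5%, so the normal approximation is closer to the printed figure.

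**3. One given time-by-score contrast at 0.004.** Unadjusted, SE = 3 × √(2/35) = 0.717, and power = Φ(2/0.717 − 2.878). With baseline correlation r, the variance 9 becomes 9 × (1 − r²).

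| Case | 35 per arm | 41 per arm |
|---|---|---|
| Unadjusted (like for like with the 80%) | 46% | 56% |
| r = 0.33 (the plan's correlation applied to baseline; assumed) | 53% | 63% |

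The unadjusted difference detectable with 80% power in one given window is (2.878 + 0.842) × 0.717 = 2.67 units at 35 per arm, or 2.46 at 41.

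**4. At least one of four windows, one score, 0.004, unadjusted.** Window estimates are taken as correlated 0.33. If the 2-unit effect is present in all four windows, the probability of at least one significant result is 82% at 35 per arm and 89% at 41. If it is present in only one window, the probability is 47% at 35 per arm.

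**5. Averaged contrast with an alpha that matches its own count, 35 per arm.**
- Three scores: 0.05/3 = 0.0167, critical value 2.394, power Φ(3.749 − 2.394) = 91%.
- One named score: 0.05, critical value 1.960, power Φ(3.749 − 1.960) = 96%.

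**The case against.** The best defence is that little is broken. The plan prints the operative threshold, it is the stricter of the two, and the sample size agrees with it. The 80% is arithmetically right. The model contains a block-type effect, and the reference to repeated measures signals what was powered. No text requires one particular window to succeed, and an any-window reading gives 82% when the effect is present throughout. Most of this stands, and it limits the point to a wrong count and an unnamed deciding contrast. It does not remove either. With a block-by-time interaction in the model, the averaged difference has to be specified as a contrast, and the any-window rule is not written down.

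The label could also be defended: one contrast at 0.0125 with the cited SD of 2.5 needs 2 × 6.25 × (2.498 + 0.842)²/4 = 34.8 per arm, also 35. But that replaces both the printed alpha and the printed SD and ignores the repeated measures, so it is the weaker reading.

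Three stronger conclusions are tempting, and the documents do not support them.
- *Type I error is inflated.* It is not if 0.004 is used for the 12 contrasts.
- *The trial is underpowered.* That holds only if a given window must succeed or the benefit is confined to one window.
- *An observed difference of 2 units would be significant under one threshold and not the other.* At 35 per arm, unadjusted, the critical differences are 2.06 (at 0.004) and 1.79 (at 0.0125), so 2 lies between. But the plan adjusts for preoperative pain. The 0.004 limit falls to 2.878 × 0.677 = 1.95 with r = 0.33, and to 1.91 at 41 per arm unadjusted, so 2 units then passes both.

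**Conclusion.** The stated basis for the threshold is wrong as written: 4 comparisons do not give 0.004 at a family level of 0.05, and 12 do. The evidence favours correcting the count. The 80% is not an error, but with the printed inputs it describes a difference averaged over 3 measures. For one given time-by-score contrast the comparable figure is about 46% at 35 per arm (56% at 41), or 53% (63%) if preoperative pain is assumed to correlate 0.33 with each window. These figures rest on the plan's SD and correlation, two-sided tests and the normal approximation. This should be fixed. It does not undermine the design.

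**What to change.** Before unblinding:

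1. **Make count and threshold agree.** By default, write alpha = 0.0042 (0.05/12: 4 times × 3 pain scores). First reconcile the number of times. Section 4.0 describes 12-hour intervals over 72 hours (72/12 = 6), and Table 6 in section 10.0 has seven rows, against four times in section 11.0. With three scores those would give 0.05/18 = 0.0028 or 0.05/21 = 0.0024. Moving from 0.004 to 0.0042 barely changes power (46.4% to 47.0% for one contrast at 35 per arm).

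2. **Name the deciding contrast, with its matching alpha and power.**
 - *If the per-window contrasts decide:* say whether any one window is enough, and restate power as about 46% at 35 per arm (56% at 41) for one given contrast before baseline adjustment. Any credit for the covariate needs a stated correlation.
 - *If the averaged contrast decides:* set alpha by the number of averaged contrasts (three scores: 0.0167, about 91% power at 35 per arm; one named score: 0.05, about 96%). Make the per-window contrasts secondary. Keeping 0.004 here would apply a 12-test correction to a contrast outside those 12.

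The cost is a few sentences of text and no change in sample size. The first choice shows less favourable power. The second makes per-window claims secondary and responds weakly to a benefit confined to one window. For an average over the four listed times, SE = √(2 × 4.4775/35) = 0.506 and the averaged effect is 2/4 = 0.5, so power is only about Φ(0.5/0.506 − 2.394) = 8% at 0.0167 and 17% at 0.05.

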## 6.0 Number of Subjects

We will enroll and randomize 82 subjects.

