#### Follow-Up

The participant will be asked to provide their average pain score, worst pain score, and lowest pain score using a visual analog scale from 0-100 with 100 being the worst at various time points during the postoperative period. The first pain scores will be recorded before they leave the PACU on the day of the procedure. Beginning the following morning, the participant will receive a text message link sent by Twilio's secure server that opens a survey housed in RedCap. The first text message will arrive at 9:00 AM and will follow the schedule in Table 6.

They will receive a text message from a secure server asking the average pain questions as well as what medications they took for pain (including medication name, dosage, and frequency). The set of questions will state what time window (example:

12:00 AM midnight the night prior to 12:00 PM noon the same day) to consider when answering the questions. If the participant has been discharged from the hospital, they will answer these questions in the text message each day. If they are admitted to the hospital at this point in time, the information will be gathered from their chart for medications and asked verbally for pain scores. Range of motion and terminal knee extension will also be recorded at the in-person postoperative follow up visits.

If the participant is unable or unwilling to receive text messages, they will be provided a document to record their pain and medications for the pre-determined intervals so when a study member contacts them, they are able to relay their answers back accurately.

Table 6. Post-Op Follow Up Assessment Schedule			
Post-Op Day	Time of Text Message	Data Collection Time Period	
POD 0	Right before discharge	Waking up from surgery to discharge	
POD 1-AM	9:00 AM	Discharge to 11:59 midnight prior	
POD 1-PM	3:00 PM	12:00 AM midnight night prior to 12:00 PM noon same day	
POD 2-AM	9:00 AM	12:01 PM noon day prior to 11:59 AM midnight night prior	
POD 2-PM	3:00 PM	12:00 AM midnight prior to 12:00 PM noon same day	
POD 3-AM	9:00 AM	12:01 PM noon day prior to 11:59 AM midnight night prior	
POD 3-PM	3:00 PM	12:00 AM midnight prior to 12:00 PM noon same day	

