### 13.0 Withdrawal of Subjects

- The participant has the right to voluntarily withdraw consent from the study at any time for any reason without prejudice to his/her future medical care by the physician or at the institution. For the occasional participant who withdraws consent, the date and reason for consent withdrawal should be documented. Participant data will be included in the analysis up to the date of the consent withdrawal.
- Investigators may stop a subject's participation in the study at any time if they decide it is in the subject's best interest. They may also do this if the subject does not follow the investigator's instructions.

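### Enrolling 41 per arm covers at most 14.6% attrition, not the stated 20%: a 20% loss leaves about 33 per arm, below the plan's own 35

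*Combined protocol and SAP*

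**What the plan says.** Section 11.0 (Data Management) gives the requirement: "A sample size of n=35 participants per treatment arm (70 total) with at least 3 measures of pain provides 80% power" for a difference of 2 units, at a significance level of 0.004, with SD 3.0, compound symmetry and a within-subject correlation of 0.33. The sentence that follows sets the enrolment: "We will enroll 41 participants (82 total) in each arm to allow for up to 20% attrition".

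Section 6.0 repeats the total: "We will enroll and randomize 82 subjects". Nowhere do the documents give another attrition rate, a rule for replacing lost participants, or a different minimum number for analysis.

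**The concern.** The requirement and the allowance stand side by side and cannot both hold. If attrition reached the level the plan says it can absorb, fewer participants would remain than its own calculation calls for. A reader relying on the sentence, such as the IRB or the DSMB, would take 7 or 8 losses per arm as covered when the arm had already fallen below 35. What is at stake is the accuracy of a stated design property and, at worst, a few points of power. The validity of the analysis is not in question.

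**Working it through.** **Inputs.** Required number 35 per arm (70 total), enrolled number 41 per arm (82 total) and attrition up to 20%, all from Section 11.0. The total of 82 is confirmed in Section 6.0.

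**1. Is 35 a firm target?** The documents name no power formula, so the method here is inferred. Take a two-sided test of the difference averaged over m measures, with the normal approximation:

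- Variance of a participant's mean: SD² × (1 + (m − 1)ρ)/m = 9 × (1 + 2 × 0.33)/3 = 4.98 for m = 3.
- n per arm = 2 × 4.98 × (2.878 + 0.842)²/2² ≈ 34.5, so 35.
- Power is 79.3% at 34 and 80.8% at 35.

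The plan's 35 is therefore reproduced, as the smallest number reaching 80%. A one-sided test would give 31.

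**2. What does a 20% loss leave?** 41 × 0.8 = 32.8 per arm; 82 × 0.8 = 65.6 in total. Both fall below 35 and 70.

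**3. What loss does 41 absorb?** In whole participants per arm:

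| Lost of 41 | Share lost | Remaining |
|---|---|---|
| 6 | 14.6% | 35 |
| 7 | 17.1% | 34 |
| 8 | 19.5% | 33 |

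The limit is (41 − 35)/41 = 14.6%, the same as 12/82 when losses are equal in the two arms.

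**4. What would 20% require?** 35/(1 − 0.20) = 43.75, so 44 per arm (88 total). Multiplying by 1.2 instead of dividing by 0.8, a common slip, gives 42, which is not 41 either. The actual inflation is 41/35 = 1.171.

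**5. Illustrative effect on power.** Use the formula of step 1, with each participant contributing information m/(SD² × (1 + (m − 1)ρ)):

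| Per arm | Power |
|---|---|
| 35, three measures each | 80.8% |
| 33, three measures each, nothing from those lost | 77.7% |
| 33 with three measures, plus one score from each of 3 lost | 80.3% |
| 33 with three measures, plus one score from each of 8 lost | 84.1% |
| 33, four measures each | 83.2% |

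These figures are not the power of the planned tests, because Section 11.0 says that the difference "between block type by post-operative time and pain score type will be evaluated using a series of linear contrasts". They serve only to gauge the size of the shortfall. Steps 2 to 4 do not depend on them.

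**The case against.** The strongest reply is that a participant who drops out is not wholly lost. Section 13.0 states: "Participant data will be included in the analysis up to the date of the consent withdrawal". The Follow-Up part of Section 10.0 adds: "The first pain scores will be recorded before they leave the PACU on the day of the procedure". The mixed model can use such partial records. Three measures is also a floor: Section 11.0 lists four collection times, and with four measures the inferred formula needs only 31 per arm, so 41 could lose 10 (24.4%) and still reach 80%.

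This stands as a reason to expect little harm, but it does not make the sentence true. The plan attaches its 35 to participants with at least three measures and does not claim that its allowance rests on partial data. The mitigation has limits too. Section 13.0 deals with withdrawn consent, not with unanswered text surveys, and the PACU score is not shown to fall in the afternoon window that Section 11.0 gives for the day of surgery.

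A second reply is that 35 is itself unsettled. The level of 0.004 is labelled "Bonferroni corrected for 4 comparisons", yet 0.05/4 = 0.0125, while 0.05/12 = 0.0042. At 0.0125 the same formula needs 28 per arm, and 41 would then absorb 1 − 28/41 = 31.7%. That label is a separate inconsistency. Since 35 and 0.004 agree with each other, and 35 is the only requirement stated, it is the right yardstick for now.

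Third, if the sponsor really expects 20% attrition, rewording leaves the trial short of 35 at that rate. That is so, but the documents do not say whether 20% is a forecast, and the likely loss of power is too small to press for a larger trial on this ground.

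**Conclusion.** The point holds, with high confidence, as a minor error. Against the plan's own requirement, the enrolment protects against 14.6% attrition and not 20%; at 20% each arm is about 2 participants short. The conclusion rests only on figures in Section 11.0 and on reading the allowance as keeping 35 participants per arm. Power would fall by about 3 percentage points in the unfavourable case of step 5, and possibly not below 80% at all once partial records or a fourth measure are counted. That second statement depends on the inferred formula.

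**What to change.** As long as 35 per arm remains the target, replace the attrition sentence in Section 11.0 with:

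> Enrolment of 41 per arm (82 total) allows for up to about 14.6% attrition (6 per arm).

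Section 6.0 can stay as it is. The illustrative power figures should not go into the plan, because they describe a time-averaged comparison. If settling the label on the significance level changes the target, recompute the allowance as 1 − target/41.

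The cost is one sentence and a less favourable stated allowance. Enrolment, procedures and analysis do not change.

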# 4.0 Study Endpoints (if applicable)

- The primary endpoint will measure subjective pain scores as 12-hour intervals during the first 72 hours of the postoperative window as collected by a study team member.
- The secondary endpoints will measure total postoperative opioid consumption through postoperative day 2, as well as measure the range of motion and terminal knee extension of participants at postoperative follow-up visits.

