- Secondary outcomes include cumulative post-operative opiate consumption over time (POD 0 pm, 1 am/pm, and 2 am), and difference in range of motion between surgical and non-surgical leg at first clinic visit (7-21 days post-op) and 6 weeks PO. Associations between these secondary outcomes with block type will be evaluated using a linear mixed approach. Similar to the primary outcome, models will include fixed effects for type, time, and the interaction between block type and time. The model for cumulative opiate consumption will also include a fixed effect for intra-operative opiates received and the model for range of motion will include a fixed effect for pre-operative difference in range of motion between surgical and non-surgical leg.
- All data will be kept on a password protected MUSC server and in a REDCap database. All paper data sheets will be kept in a locked cabinet, in a locked office that only IRB approved study team members have access to. Participants will be given a study ID number that will be used to identify them throughout the study.

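### The opioid model has no stated covariance; if the pain model's single random subject effect is reused on running totals, the test of the final total is anti-conservative

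*Combined protocol and SAP*

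**What the plan says.** Section 4.0 defines the opioid endpoint as "total postoperative opioid consumption through postoperative day 2". Section 11.0 turns it into running totals at four times: "Secondary outcomes include cumulative post-operative opiate consumption over time (POD 0 pm, 1 am/pm, and 2 am".

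On the model, Section 11.0 says "Associations between these secondary outcomes with block type will be evaluated using a linear mixed approach", and then "Similar to the primary outcome, models will include fixed effects for type, time, and the interaction between block type and time". Intra-operative opiates are added as a covariate. No random effect, covariance structure, contrast or significance level is given for the opioid model.

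The only covariance term described anywhere belongs to the pain model, also in Section 11.0: "a random subject effect to account for correlation between pain scores collected on the same subject over time". The pain sample size is likewise worked out under compound symmetry. The one safeguard, placed in the pain paragraph, is "Model assumptions will be checked graphically, and transformations will be considered as needed".

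**The concern.** A running total contains every earlier total. Its variance therefore rises from one time to the next unless the amounts taken in successive windows are negatively correlated. A model whose only covariance term is a random subject effect assumes the same variance at every time, and in effect uses the average. The last total, which is closest to the Section 4.0 endpoint, has the largest variance when those amounts are non-negatively correlated, so there the average falls furthest short.

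Lower total opioid use is one of the trial's stated hypotheses (Section 1.0). If the averaged variance is used, the confidence interval for the last total is too narrow and a null block effect is declared significant too often. At the first time the error runs the other way, and a real early difference would be hard to detect.

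**Working it through.** **Plan's own figure.** The plan gives no power, SD or error rate for opioid use. Its pain calculation in Section 11.0 shows the covariance it works with: 35 per arm and 80% power for a 2-unit difference at alpha 0.004, from 3 measures with SD 3.0 and within-subject correlation 0.33.

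- SD of the mean of 3 compound-symmetric measures = 3.0 × √((1 + 2 × 0.33)/3) = 2.232.
- With a difference of 2 and two-sided alpha 0.004 (sidedness is not stated), n = 35 per arm gives 80.8% power, so the figure reproduces.
- A contrast at a single time would have 46.4% power. The stated figure is thus for the time-averaged difference under constant variance.

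**Inputs for the opioid check.** From the documents: four running totals, equal allocation, 35 or 41 per arm. Assumed, because the documents do not give them: two-sided 5%, the window variances, and the correlation r between window amounts. The value 0.33 is borrowed from pain.

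**Formulas.** Let V_k be the variance of the total after k windows. With equal window variances of 1, V_k = k + k(k − 1)r. With complete data, a random-intercept fit gives each time the mean V̄ of the four V_k. The model SE at time k is √(V̄/V_k) of the true SE, and the type I error is 2 × (1 − Φ(1.96 × √(V̄/V_k))).

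| | V_1 to V_4 | V̄ | SE ratio, last total | Type I, last total |
|---|---|---|---|---|
| r = 0 | 1, 2, 3, 4 | 2.5 | √(2.5/4) = 0.79 | 12.1% |
| r = 0.33 | 1, 2.66, 4.98, 7.96 | 4.15 | √(4.15/7.96) = 0.72 | 15.7% |

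For the first total, 1.96 × √(2.5/1) = 3.10 gives 0.2% at r = 0, and it is lower still at r = 0.33. For the third total, V̄/V_3 = 2.5/3 = 4.15/4.98 = 0.833 in both rows, which gives about 7%.

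**Simulation.** With 20,000 trials at 35 and at 41 per arm, the last total had 12.2-12.7% (r = 0) and 15.4-16.0% (r = 0.33). A small set of mixed-model fits with an intra-operative covariate (150 per setting) gave mean model SEs of 0.378 against a true 0.478, and 0.493 against 0.674. These are ratios of 0.79 and 0.73. That set is too small to fix the error rate but confirms the SE shortfall.

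**Other assumptions, last total, nominal 5%:**

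- Window SDs halving each time: 6.0-8.8% (r = 0 to 0.5).
- First-window SD three times the rest: 6.7-11.0% (r = 0 to 0.5).
- SDs 1, 0.8, 0.6, 0.4: 8.2% (r = 0) to 12.4% (r = 0.5).
- Equal windows, r = 0.5: 16.6%.
- Skewed counts: about 17%.
- SDs 1, 2, 3, 3: 18.0-21.0% (r = 0 to 0.5).
- Equal windows, r = −0.2: V_k = 1, 1.6, 1.8, 1.6 and V̄ = 1.5, giving 5.8%.

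**Other tests in the same model (simulated).** The block-by-time test had 7-10%. The block effect averaged over time had 4.7-5.4%. With window amounts w1 to w4, however, that average equals w1 + 0.75 w2 + 0.5 w3 + 0.25 w4, which weights early use more heavily and is not the total.

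**With a separate variance at each time**, or one comparison of the final total, the last-total test had 4.8-5.1% in every simulated scenario.

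**The case against.** The strongest reply is that the plan never says the opioid model has a random intercept only. The sentence that refers back to the primary outcome lists fixed effects, the random subject effect is written for pain scores, and compound symmetry appears only as a power assumption. An analyst could fit an unstructured covariance without departing from the text. This stands, and it makes the error conditional. It does not remove the point: reusing the pain model is the natural reading, and otherwise the plan leaves open the choice that decides whether this test is valid.

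Second, no opioid contrast is named, and the time-averaged block effect is about valid. That also stands, but that effect does not answer an endpoint defined as a total.

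Third, assumptions are to be checked. The check is written for pain, its only stated remedy is transformation, and a transformation would change the quantity estimated from a difference in mean total use. No alternative covariance is offered.

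A reader might infer that the plan as written commits to a 12-16% error rate, that running totals produce it whatever the data look like, or that opioid use is the trial's main supporting claim. The documents support none of these. They give no opioid SD, correlation or alpha. Negative correlation between windows can remove the inflation. Section 1.0 lists pain, opioid use and range of motion without ranking opioid use above the rest.

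**Conclusion.** The point holds in conditional form. If the pain model's single random subject effect is carried over, the standard error for the last running total is too small whenever window amounts are non-negatively correlated. The type I error of that contrast is about 12-16% at a nominal two-sided 5% with four equal-variance windows and correlation 0 to 0.33, and roughly 6-21% across the other patterns examined. The equal variances, the correlation and the 5% level are assumptions. The late totals and, mildly, the block-by-time test are affected; the first-total contrast is conservative.

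This should be fixed, but it concerns a secondary outcome and does not touch the pain analysis. Separately, the last modelled time is the morning of postoperative day 2. That stops short of the Section 4.0 endpoint, which runs through that day, and of the 72 hours in Sections 1.0 and 3.0, so even a correct standard error would belong to a shorter total than the one defined.

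**What to change.** In the secondary-outcome paragraph of Section 11.0, specify an unstructured covariance (a separate variance at each time) for the opioid model, keep the intra-operative opiate covariate, and name the block contrast at the final total as the test of total use. State its significance level.

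Two alternatives would also serve:

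- Compare the final total as one value per participant, adjusted for intra-operative opiates, with robust standard errors.
- Model the amount in each window with an unstructured covariance and report the total as the sum of the window contrasts.

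In the same edit, reconcile the last modelled time with Section 4.0 and with the 72 hours in Sections 1.0 and 3.0.

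The cost is SAP wording and a wider interval for the total. The one-value version also needs a rule for participants with a missing window, since the plan allows for up to 20% attrition.
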